### **Participants**

Participants will complete their first visit with research staff at Penn State Hershey or signed exercise sites (60 minutes baseline visit plus 30 minute DXA scan, if applicable).

Prior to the baseline visit, research staff will send participants the following questionnaires, to be completed at home and brought with them to the baseline assessment: sociodemographic and past medical history, fear of falling, falls history (BRFSS), self-reported health, PROMIS 29: depression, anxiety and physical function, fatigue, pain, sleep disturbance, ability to participate in social roles and activities, brief loneliness questionnaire, physical activity, social domain (caregiver), and assistive devices. These surveys should take approximately 20 minutes to complete.

Research staff will review the informed consent document and the liability waiver with individual. Before enrolling the individual (signing the informed consent and liability waiver), a research staff will take the individual's blood pressure and heart rate to screen for eligibility.

- If blood pressure is  $\geq 180$  systolic OR  $\geq 110$  diastolic OR heart rate is  $\geq 120$  bpm, research staff will suggest the individual to see a PCP to control their blood pressure or heart rate, and if they would like to still participate in our study they would have to receive PCP permission before re-screening for eligibility.
- If blood pressure is between 160 to 179 systolic OR 100 to 109 diastolic AND heart rate is  $<120$  bpm, research staff will provide critical value letter to individual and suggest him/her to see a PCP about their high blood pressure, but they will still be enrolled into the study.

If the individual is eligible, based on their blood pressure or heart rate results (above), a research staff will ask if they have any questions about the consent and liability waiver, and if they agree, both the research staff and participant will sign. The participant will be provided with a copy of the signed consent liability waiver for their records.

Research staff will take the participant's baseline measurements: (1) height and weight, (2) blood pressure and heart rate, (3) 30 second chair stand test, 30 second bicep curl test. Research staff will also review participant's medications.

Research staff will remind participants that they may skip any questions that they prefer not to answer. To assure that the participant can safely be part of the study, critical clinical information (e.g., high blood pressure, depression screen) will be communicated to the PCP and participant.

Research staff will recommend participants review the fall risk brochures from Centers for Disease Control and Prevention (CDC) on preventing falls, checking for safety and staying independent.

If PCP authorized a DXA scan, a research staff will take the participant to the DXA center for a Dual-energy X-ray absorptiometry (DXA) scan.

After completing the baseline visit, each participant will receive \$25.

If blood pressure is  $\geq 180$  systolic OR  $\geq 110$  diastolic OR heart rate is  $\geq 120$  bpm at the baseline assessment (post-consent), research staff will suggest the individual to see a PCP to control their blood

pressure or heart rate, and if they would like to still participate in our study, they would have to receive PCP permission before completing the baseline visit and continuing with the study.

#### Spanish Speaking Interview Members

60 minute individual interview will be conducted over the phone. A Spanish speaking member of our team will facilitate the interviews and we will audio record the sessions for translation and data analysis purposes. The facilitator will use the interview guide to lead the discussion/interview. The interview guide will include the following: (1) How best to design the Band Together intervention for the Spanish population? (2) How best to interest potential participants? (3) What concerns exist about participating? (4) How to design a recruitment within the Spanish population and (5) How would you change/update the current Band Together intervention material to be better suited the Spanish population. Participants will be given a \$50 stipend.

#### **7.2.6.1. Baseline Dual-energy X-ray absorptiometry (DXA)**

##### **Participants**

The National Osteoporosis Foundation Guidelines suggest a DXA in postmenopausal women and men over 50 who have a fragility fracture. As part of standard of care, patients in the study are asked to have an AXIAL (Central) DXA scan, if their PCP thinks it is clinically indicated. Patients, WILL be billed as they normally would in a clinical setting.

In addition, as part of research, we will be asking the participants to do a total body DXA scan to measure body composition. For this scan, [name], chair for the Department of Radiology, had agreed to do it at no cost to the research. Results from the total body scan will be placed in the participants' EHR. This optional scan will be performed the same way at all institutions (Penn State Hershey, University of Pittsburgh, and Temple University). Patients will NOT be billed for this DXA scan. Radiation exposure is reported in the consent form.

We will ask that the patient have the DXA done at Penn State Hershey Medical Center. We are currently working with [name] and his team, which use the same DXA machine (Hologic) as our other study sites. The participant's PCP will receive a faxed report with the test results, as they would usually.

If PCP authorized a DXA scan, a research staff person, during the baseline visit, will take the participant to have their DXA scan. We will remind the patient 2 days before of their DXA appointment. The DXA scan will take about 30 minutes.

If the participant has received a DXA scan within 2 years of their baseline visit date and the research staff has obtained the records either through the participant or the participant's PCP, the DXA scan results are able to be analyzed. If the DXA results are received via the participant's PCP prior to the participant's baseline visit, the research staff person will obtain consent from the participant to analyze the DXA report.

#### **7.2.6.2. Communicating Baseline Measurements**

We will communicate the results of any critical values of a baseline measure (e.g., Blood pressure, Depression screener) and fracture risk and treatment recommendations to both the patient/group

leader and primary care provider. These are considered enhancements to usual care, as most patients who suffer a FF are never tested or treated, and to maximize patient safety (29, 30).

### **7.2.6.3. Randomization**

Once eligible participants who sign the informed consent and completed the baseline questions, research staff at each site will randomize the participant into one of two groups (control, enhanced usual care; or intervention groups, enhanced usual care plus coached exercise program) in a one-to-one ratio. Stratification factors for randomization will be study site location (1=Penn State, 2=University of Pittsburgh, 3=Temple University), gender (0=female, 1=male), and bisphosphonate and other potent medication use (0=never, 1=ever). The research staff will conduct the randomization during the baseline visit through REDCap.

Participants randomized to the intervention group will also receive an introductory letter from their exercise coach with picture/name and details on a forthcoming phone call.

Group leaders, community members, and Spanish Speaking Interview members will not be randomized.

#### **Group A: Control Group- *Enhanced Usual Care Intervention***

Research staff will review the three printed pamphlets on fall risks and exercising during baseline. We will recommend the control group to exercise. However, they will NOT be able to participate in our exercise program intervention. Control group participants will receive information about exercise from the Centers for Disease Control and newsletters about fall prevention that include exercise. They are encouraged to exercise, though they are not invited to Band Together, nor will they receive one-on-one support from our coaches. We will not ask people to abstain from any form of exercise.

In addition, to enhance the usual care intervention and maximize patient safety, the baseline bone density results (measured by Dual-energy X-ray absorptiometry, DXA) will be communicated to their PCP, and any *critical* values of a baseline measure (e.g., Blood pressure, Depression screen) to both the patient and primary care provider.

#### **Group B: Exercise intervention Group - *Enhanced Usual Care plus Exercise Coaching Intervention***

At baseline, the exercise group will receive the three printed pamphlets on fall risks and exercising in groups (same as the controls) plus:

- An *exercise program* that includes strength, balance, and aerobic exercises
- An *exercise coach* that provides in-person, email, and/or telephone support/feedbacks to enhance participation in the exercise program
- *Regular progress reports* sent by coaches to the participant's primary care provider by fax/EHR every 6 months, to communicate the patient's progress.
- *Paper-based Exercise Trackers* will be given to help exercise coaches review the participant's progression with strength exercises

If any Group Leader or Participant is hospitalized and/or absent for 6 consecutive weeks or more and wants to return to the exercise sessions, Research Coaches will complete a return to exercise protocol with the individual. The Coach will ask if the Group Leader or Participant has had a hospitalization or a major change in their health since their last exercise session. If the Group leader or Participant answers yes, Research Coaches will ask about the event, hospitalization, and current health status and report the event as an Adverse Event in REDCap. A Principal Investigator will review the case and may request that the Group Leader or Participant obtain PCP permission

before returning to the exercise program. In all cases, Group Leaders and Participants will be instructed to “Start Low and Go Slow” upon resuming exercise: starting at a lower resistance band, and slowly working their way back to the level at which they were exercising before their absence or hospitalization.

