### 1.2 Primary Study Endpoints

#### **Serious Fall-Related Injuries (SFRI), including Fragility Fractures from a fall**

To identify our main outcome (SFRI, including FF), we will collect main outcome data every 4 months and during the assessment (12, 24, 36 months) using a fall calendar to record all fall events (e.g., date, location). This will help participants to recall falls during the 4 month period. Subjects will be asked, for example, *“Have you fallen in the past 4 months (or since last contact)? Were you injured in any fall in the past 4 months (or since last contact)?” “Did you land on the floor, ground or other lower level when you fell?” “When you fell, did you break or fracture a bone? or “Were you told by a doctor, or other health professional”*. For any new events, the circumstances regarding the incident (i.e., what occurred) will be recorded for use in adjudicating whether the injury was related to a FF (i.e., “low-trauma” or fall from standing height or less). The dates of injuries and the name of the institution will be recorded, so that medical records can be sought using the authorization form signed by all patients at baseline.

For any SFRI (including FF) or hospitalization/ED visits noted quarterly or during the 12, 24 or 36 months assessment, medical records will be obtained, including outpatient notes, emergency department notes, hospital discharge summary reports and radiologic notes. All outcomes (e.g., SFRI) require evidence from medical records to be counted.

These records will be collected and presented, blinded to treatment condition, 14 days before the monthly meeting to the Outcomes Committee ([name]-Chair, [name], [name], [name], [name]). For each event, the Outcomes Committee will be charged with determining whether it was 1) a fracture related to a fall from standing height or less, 2) a non-traumatic fracture not related to a fall, 3) a serious fall related injury without a fracture, 4) a traumatic fracture (e.g., MVA), 5) a non-serious fall related injury, or 6) none. A vote is made for each event. If there is not agreement, it will be opened for discussion and another vote. If

consensus is not possible, the case will be presented to [name] [name] for final adjudication, given her vast experience with this process (34, 77, 78).

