##### **Community Members:**

The screening will be completed over the phone. People who call will be screened by a research staff based on the eligibility criteria. Research staff will ask interested community members for authorization to contact PCP during this time. If the person is eligible, we will ask the community member to obtain PCP permission in order for them to participate. If the community member has completed enrollment in the WISE study, has been active in the Band Together program within the past 6 weeks and has had no change in health status since they last exercised, PCP permission will be carried over from the WISE study and not be reobtained.

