### **Exercise coaching**

For the first 4 weeks of the intervention the coaches will:

- a. After randomization occurs, the coach will call participants in the intervention group for introduction and to learn more about the participant and any medical conditions that may be important for the exercise coach to know. If the coach learns of any serious medical events or hospitalizations since baseline they will follow the return to exercise protocol and present the case to a PI through adverse event reporting in REDCap.
- b. Contact the patients by weekly phone calls or during site visits(duration of call: approximately 5 minutes) to give exercise tips, discuss goals and progress toward goals, injuries, soreness, and enjoyment.
- c. Conduct site visits to assure program fidelity, provide quality control feedback to volunteer Group Leaders.

For weeks 4-8 of the intervention coaches will follow item b, but instead of every week they will perform them bi-weekly.

After the 8th week of intervention coaches will follow items b & c, performing these items every month.

The coaches will meet regularly with group leaders and will supervise sessions on a rotating basis. If the participant misses 3 consecutive classes without notifying exercise coach, or the group leader expresses concerns for a participant, the coach will perform a check-up call between the regularly scheduled calls. Coaches will provide ongoing support and monitor the safety of the program for all participants.

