#### **18.4 Reporting of Adverse Events (AE) and New Information**

All potential AEs that are brought to the attention of the research staff will be passed on to the site PIs. At each research institution, the site PI will determine the likelihood that the AE is due to the study. AEs will be reported to the IRB if the harm was unexpected AND likely/probably related to the research

Site project managers will be responsible for communicating all site adverse events to the core project manager. The core project manager will review all adverse events and place them into categories to be reviewed by the data and safety monitoring team during the bi-annual meeting (described in section 10).

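### Once sessions are under way, a fracture or other serious event treated without admission does not by itself require a review before return to exercise within 6 weeks

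*Combined protocol and SAP*

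**What the plan says.** Two parts of Section 7.2.6.3 set the trigger.

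Under the Group B heading, for people already exercising, the protocol is completed "If any Group Leader or Participant is hospitalized and/or absent for 6 consecutive weeks or more and wants to return to the exercise sessions". The coach then asks whether the person "has had a hospitalization or a major change in their health since their last exercise session". A yes leads to questions about the event, an adverse event entry in REDCap and review by a Principal Investigator, who may ask for PCP permission. Everyone who goes through the protocol is told to restart on a lighter band, "slowly working their way back to the level at which they were exercising before their absence or hospitalization".

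Under Exercise coaching, item a governs the introductory call after randomization and starts from a wider set of events: "If the coach learns of any serious medical events or hospitalizations since baseline they will follow the return to exercise protocol". The case then goes to a PI. Item a is not repeated. Item b (coach contacts, which cover injuries and soreness) continues bi-weekly in weeks 4 to 8, and items b and c (site visits) continue monthly after week 8. Neither carries a return-to-exercise step.

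Section 1.2 foresees serious injuries managed outside an inpatient stay. When one is reported, "medical records will be obtained, including outpatient notes, emergency department notes", along with discharge summaries and radiology notes.

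**The concern.** A serious event without admission is enough for PI review if it is found at the introductory call. The same event during the following 36 months is not, unless the person stays away for 6 weeks. The question that would pick it up is asked only after the narrower trigger has been met.

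At stake is the safety of individuals. Every randomized participant has had a fragility fracture, the sessions combine resistance-band and balance work, and Section 11 names injury from exercising as the foreseeable risk. A person with a recent fracture could resume that work under the protocol as written with nobody obliged to judge fitness first or to lower the resistance.

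**Working it through.** There is no plan figure to reproduce. The check is a comparison of text, followed by a partial sizing.

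**1. The two triggers.**
- Introductory call (Exercise coaching, item a): serious medical event, or hospitalization. It covers intervention participants only.
- During participation (Group B): hospitalization, and/or absence of 6 or more consecutive weeks. It covers participants and group leaders.

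An absence test cannot apply at the introductory call, which explains one difference. It does not explain why serious medical events are missing from the later list. If the 6 weeks were read as qualifying hospitalization too, the later trigger would be narrower still.

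**2. A test case.** A participant fractures a bone in a fall, is treated in the emergency department, goes home, and returns after 4 to 5 weeks. Not hospitalized: first limb not met. Absent for less than 6 weeks: second limb not met. The protocol does not start, so the question, the PI review and the lighter-band instruction are not required.

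**3. Is there another required step before return?**
- Missed-class call. At three sessions a week, 4 to 5 weeks is 4 × 3 = 12 to 5 × 3 = 15 missed classes, assuming full attendance otherwise. The rule applies "If the participant misses 3 consecutive classes without notifying exercise coach", or if the group leader is concerned. So the coach would either make the call or already know of the absence. The call has no return step.
- Regular coach contacts: injuries are discussed, with no return step.
- Adverse event route (Section 18.4): the event goes to the site PI, but the stated task is that "the site PI will determine the likelihood that the AE is due to the study". That is a judgement of relatedness, not of fitness to resume.
- Monitoring team (Section 10): it can deliver corrective action on individual events, but its meetings are bi-annual.
- Outcome calls (Section 7.2.7): every 4 months, so a call may come after the return.
- Removal (Section 3.3.1): discretionary.
- Leader training (Section 7.2.3) and individualized exercise (Section 11): general measures, not a review of the case.

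None of these must happen before the person resumes.

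**4. Group leaders.** The introductory call and the missed-class rule are written for participants. For leaders the Group B trigger is the only stated one, supplemented by a coach contact every 3 months (Section 7.2.7) and the coach's regular meetings with them.

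**5. What can be sized.** Inputs: 1,130 randomized one to one (Sections 8.1 and 7.2.6.3); 36-month rates of 7% with exercise and 13% in controls (Section 8.3).
- Exercise arm: 1,130 / 2 = 565.
- First serious fall-related injuries at the planned rate: 565 × 0.07 = 39.55, about 40.
- If exercise had no effect: 565 × 0.13 = 73.45, about 73.

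These are all first injuries in the arm across three sites, with all 565 taken as exercising. They include people admitted, people away 6 weeks or more (both already covered) and people who never return. They exclude repeat events, other serious medical events, and events among about 350 group leaders (Section 8.1), for which no rate is given. The range therefore indicates part of the review workload. It neither estimates nor caps the number in the gap, which would need the share treated without admission and the time away. The documents give neither.

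**The case against.** The strongest reply is that the threshold was chosen. Section 7.2.5 (Participants) asks about hospitalization and major health change only after a delay of 6 weeks or more between PCP permission and the scheduling of the baseline visit. Section 5.1.2 asks a community member for PCP permission after 6 weeks of inactivity. A 6-week gate is thus a recurring device, and Group B adds hospitalization as an immediate trigger. The introductory call is also a different setting: the coach does not yet know the person and no exercise has begun. Afterwards the coach has regular contact, works on progression and form, and runs monthly fitness tests.

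Much of this stands. A reader might infer that the plan contradicts itself, or that serious medical events were dropped by mistake. The documents do not support that. Section 7.2.5 (Community Members) points the other way, since a completer keeps PCP permission only if active "within the past 6 weeks and has had no change in health status since they last exercised", but that concerns permission on joining a new category without a coach. It shows only that the plan can treat a health change as sufficient in itself.

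A reader might also infer that such injuries go unseen, or that people do resume on recent fractures. Neither is shown. The event would often be known, and no text indicates when injured participants come back.

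It is also fair that PCP permission is optional even when the protocol runs. The gain is a required PI look and a lighter-band restart, not medical clearance.

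What the reply does not supply is any required step before return in the test case. A deliberate threshold still leaves that case uncovered.

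**Conclusion.** The point holds in a limited form. As written, the protocol allows a participant or group leader to return within 6 weeks of a fracture or other serious event treated without admission, with no required PI review and no required restart at lower resistance. Existing contacts and discretion make it likely that someone would know and could act, but do not oblige anyone to.

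It is a minor safety alignment, worth making because it is cheap. The number affected cannot be stated. It would be wrong to take it as a threat to the trial's inference: alpha, power and the primary analysis do not depend on this trigger.

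The conclusion rests on two assumptions: that the Group B trigger means what it says, and that no unpublished instruction adds the missing step. Section 16.5 mentions a working protocol of study procedures, which could contain one. If it does, the remaining task is to bring that text into the protocol.

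**What to change.** In the Group B paragraph of Section 7.2.6.3, keep the two existing limbs and insert a third: the person reports a fracture or other serious medical event, whether or not admitted. Extend the restart instruction so that it covers return after such an event as well. Leave PCP permission to the PI's discretion, as now.

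Use this coach-level wording and not serious fall-related injury. That category is assigned from medical records by the blinded Outcomes Committee at monthly meetings (Section 1.2), so a coach cannot apply it when someone asks to come back. Serious medical event is already the term coaches use at the introductory call. The plan does not define it, so naming fracture gives coaches one concrete anchor.

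Costs: two wording changes and a modest number of extra PI reviews, drawn from an unknown part of the 40 to 73 first injuries plus an unknown number from repeat events, other serious events and group leaders. No new assessment is needed. Because coaches serve only the exercise arm, the change also adds slightly to adverse event logging in that arm. Endpoint events should therefore still be ascertained through the 4-monthly calls and medical records used in both arms.
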